7.2.11. Response Assessments

With the exception of prostate cancer subjects in Parts E and F, post-baseline response assessments in this trial are to be performed every 9 weeks (-10 days).

- For q3w subjects: Response assessments will be performed within 10 days of C4D1, C7D1, C10D1, and every three cycles thereafter.
- For q6w subjects: Response assessments will be performed approximately every 1.5 cycles, i.e., mid-Cycle 2, end of Cycle 3, mid-Cycle 5, end of Cycle 6, etc.

For prostate cancer subjects in E and F, post-baseline response assessments and a bone scan will be performed every 12 weeks (-10 days), i.e., within 10 days of C3D1, C5D1, C7D1, and every two cycles thereafter.

The imaging interval may be increased to every 12 weeks with a +/- 3 week window for subjects who remain on study treatment for ≥ 24 months

7.3. Assessments for Subjects in Part C After Adding Post-Progression Nivolumab

7.3.1. Cycle X Day 1

The following evaluations and procedures will be performed during this visit (± 3 days):

- Physical examination.
- Vital signs pre-and post-infusion.
- Weight.
- ECOG performance status.
- Pregnancy test for WOCBP.
- 12-lead ECG.
- Laboratory assessments: Chemistry, hematology, coagulation, thyroid function, and urinalysis. Laboratory assessments need not be repeated if they were performed within 72 hours of the Day 1 visit.
- Blood samples for PK.
- Record concomitant medications.
- Adverse events assessment.
- JTX-2011 Administration followed by observation for at least 1 hour.
- Nivolumab or pembrolizumab administration followed by observation for at least 1 hour.

7.3.2. Cycle X Days 22 (q6w Subjects Only)

The following evaluations and procedures will be performed during this visit (± 3 days):

- Physical examination.

- Vital signs pre-and post-infusion.
- Weight.
- ECOG performance status.
- 12-lead ECG.
- Laboratory assessments: Chemistry, hematology, and coagulation.
- Record concomitant medications.
- Adverse events assessment.
- Nivolumab or pembrolizumab administration followed by observation for at least 1 hour.

7.4. End of Treatment (All Parts)

At the end of treatment (within 28 days \pm 7 days after last dose of study drug):

- Physical examination.
- Vital signs.
- ECOG performance status.
- 12-lead ECG.
- Laboratory assessments including chemistry, hematology, coagulation, thyroid function, and urinalysis.
- Prostate cancer subjects in Parts E and F only:
 - PSA
- Blood samples for Target Engagement, PK/ADA/NAb (not required for Part C subjects receiving nivolumab or pembrolizumab post-progression).
- CT Scan for response assessment (unless performed within 9 weeks of End of Treatment visit [within 12 weeks for prostate cancer subjects]).
- Record concomitant medications.
- Adverse events assessment.

7.5. Long-Term Follow-up

Long-term follow-up assessments will be done every 12 weeks (\pm 2 weeks) from the last dose of JTX-2011. All subjects who discontinue study treatment will be followed for:

- Survival: Via telephone or email until a) death, b) withdrawal of consent, c) they are lost to follow-up, d) the Sponsor notifies sites that survival follow-up is no longer required, or e) termination of study by the Sponsor
- Assessment of treatment-related SAEs until resolution to baseline or Grade 0-1.

Subjects discontinuing treatment due to reasons other than documented disease progression will have their tumor assessed (using the same modality that was used during study treatment) every 12 weeks (\pm 2 weeks) for up to 2 years after the last treatment visit, until a) they start a new therapy for their cancer, b) death, c) withdrawal of consent, d) are lost to follow-up, e) the Sponsor notifies sites that tumor assessment is no longer required during long-term follow-up, or f) termination of study by the Sponsor.

8. DESCRIPTION OF STUDY ASSESSMENTS

8.1. Demographics

The following demographic data will be obtained for each enrolled patient: year of birth, gender, ethnicity, and race.

8.2. Medical History

A detailed medical history will be taken at Screening. Significant relevant Medical History within the past 5 years, including smoking history, will be recorded. Disease related history, including known status of relevant gene aberrations or over-expression or viral status should be included (e.g. BRAF, EGFR, HER2, MSI, Epstein Barr Virus, Human Papilloma Virus)

8.3. Physical Examination

A full physical examination (outlined by institutional guidelines), including weight with height (Screening only), will be performed at Screening and End of Treatment visits by a qualified individual. At all other visits, a targeted physical exam will be performed per institutional guidelines.

8.4. Vital Signs

Measurements of vital signs include blood pressure (BP), temperature (T), heart rate (HR), and respiratory rate (RR), oxygen saturation (SpO₂).

8.5. Weight

The determination of JTX-2011 dose will be based on the subject's weight.

8.6. Eastern Cooperative Oncology Group (ECOG) Performance Status

The ECOG performance status assessment should be assessed according to Section 12.3.

8.7. Response Assessment

The anti-tumor activity of study treatment will be assessed using RECIST v1.1 criteria, modified RECIST for subjects with mesothelioma only {Byrne 2004} and PCWG2 guidelines for subjects with prostate cancer only {Scher 2008} as assessed by study investigators and independent central radiology review. Imaging for efficacy assessments will be performed approximately every 9 weeks with the exception of subjects with prostate cancer who will have imaging assessments every 12 weeks with both CT and bone scans; prostate cancer outcomes to be assessed per the PCWG2 guidelines. The imaging interval may be increased to every 12 weeks with a +/- 3 week window for subjects who remain on study treatment for ≥ 24 months.

Immune-related response criteria (irRC) {Wolchok 2009} will also be assessed by independent central radiology review as well as study investigators where feasible.

8.8. Clinical Laboratory Evaluations

All clinical laboratory assays (e.g. Chemistry, Hematology, Coagulation, Urinalysis, pregnancy testing, and Thyroid function) will be performed at local laboratories according to the laboratory's normal procedures. Results will be reported by Investigators in the eCRF. Abnormal laboratory values which are unexpected and not explained by the subject's clinical condition should be repeated until confirmed, explained, or resolved. Changes starting from the initiation of study drug (e.g. JTX-2011 monotherapy or in combination with nivolumab, ipilimumab or pembrolizumab) exposure will be recorded as an adverse event if clinically significant in the judgement of the Investigator. Clinical Laboratory evaluations are summarized in Table 6.

Table 6: Clinical Laboratory Evaluations

Panel	Parameters
Chemistry	Calcium Chloride Total Protein Potassium Glucose Sodium Blood Urea Nitrogen (BUN) Creatinine AST (SGOT) ALT (SGPT) Alkaline Phosphatase (ALP) Bicarbonate Lactate Dehydrogenase (LDH) Albumin Direct Bilirubin Indirect Bilirubin Total Bilirubin Phosphorus Magnesium Uric Acid
Hematology	Calculated ANC WBC RBC Hemoglobin Hematocrit Platelet count Neutrophils Lymphocytes Monocytes Eosinophils Basophils
Coagulation	Prothrombin Time (PT) International Normalized Ratio (INR) Activated Partial Thromboplastin Time (aPTT)

Panel	Parameters
Thyroid Function	Total T3 Free T4 TSH
Urinalysis	Dipstick: pH Glucose Protein Bilirubin Ketones Leukocytes Blood Microscopic (if dipstick is positive): WBC RBC Casts
Other	PSA (for subjects with prostate cancer only)

8.9. Pharmacokinetic (PK) Sampling

Plasma PK for JTX-2011 will be collected in ALL parts this study. (See Section 12.1).

Plasma PK for nivolumab, ipilimumab, and pembrolizumab will be collected in the relevant parts of the study.

Pharmacokinetics of JTX-2011 in Parts A and B will be used to inform initiation of the Safety/PK/PD Expansion Cohorts.

If emerging PK data show that a less frequent sampling schedule is warranted, PK sampling may be reduced without a protocol amendment.

A separate Laboratory Manual detailing the PK sample collection, preparation, storage and shipping process will be provided.

8.10. Biomarkers

Biomarkers assessed in this study are summarized in Table 7.

Table 7: Biomarkers

Biomarker	Sample	Purpose
Pharmacodynamics: • Target Engagement	Blood	Inform dose and schedule decision for expansion cohorts
Safety: • Cytokines • Anti-drug Ab and neutralizing Ab for JTX-2011, nivolumab, and ipilimumab	Blood	Assess potential cytokine induction Anti-drug Ab may affect safety and/or efficacy
Potential predictive biomarkers: • ICOS expression by IHC	Archival/fresh	Stratification, correlation with efficacy
• PD-L1 IHC	Archival/Fresh	Explore correlation with efficacy

Biomarker	Sample	Purpose

 • Predefined ICOS RNA signature 	Archival/Fresh	Explore correlation with efficacy

 • DNA for mutational load and neoantigen pre-treatment 	Archival/Fresh	Explore correlation with efficacy
Exploratory: 
 • RNA signature (Nanostring® or RNAseq) 	Blood/Archival/Fresh	Identify potential predictive gene signature AND assess JTX-2011 induced changes in gene expression

 • Multiplex IHC for Immune cell subsets pre-and post-treatment 	Fresh biopsy	Assess changes in T cell infiltrate in tumors after treatment

 • Immunophenotyping 	Blood	Assess effect on peripheral T cells

Please refer to the separate Laboratory Manual detailing the pharmacodynamics sample collection times, preparation, storage and shipping process.

ICOS target engagement (TE), a pharmacodynamic biomarker, will be collected and used to determine RP2D and schedule.

JTX-2011 is not expected to induce changes in inflammatory cytokines (safety) or peripheral immune cells (exploratory), but both measures will be assessed. Anti-drug antibodies to either JTX-2011, nivolumab, ipilimumab, or pembrolizumab may impact efficacy and/or safety, and will be measured throughout the study.

Archival tumor tissue samples will be assessed for expression of ICOS and PD-L1 as potential predictive markers of response to JTX-2011 monotherapy and in combination with nivolumab, ipilimumab, or pembrolizumab, which will be correlated with efficacy outcomes. Potential predictive biomarkers in both archival and fresh tumor specimens, including but not limited to protein assays such as ICOS IHC, RNA assays such as but not limited to predefined ICOS gene signature, novel gene signature as measured by assays such as but not limited to Nanostring®, and DNA based assays of mutational burden, will be assessed at baseline and correlated with efficacy outcomes, if sufficient samples are available. Potential predictive biomarkers in peripheral blood, including RNA profiling and DNA based assays of mutational burden, will be assessed at baseline and correlated with efficacy outcomes, if sufficient samples are available. Paired pre-and post-treatment biopsies will be analyzed for changes in immune cell related gene signatures and immune cell infiltrates, specimens permitting. These will assess the effect of different doses of JTX-2011 on intratumoral immune cell changes that are expected to correlate with efficacy, in order to inform the best dose for continued clinical development.

If emerging pharmacodynamic data show that a less frequent sampling schedule is warranted, biomarker sampling may be reduced without a protocol amendment.

8.10.1. Collection of Biopsies

8.10.1.1. Archival Tissue Collection

As described above, multiple markers will be reviewed in archival tissue. All subjects enrolled in this trial are required to submit archival tumor tissue samples, unless archival material is unavailable (e.g., all tumor blocks are exhausted). These samples will be assessed for expression of ICOS and PD-L1 as potential predictive markers of response to JTX-2011 monotherapy and in combination with nivolumab, ipilimumab, or pembrolizumab, which will be correlated with efficacy outcomes. If sufficient sample is available, additional testing will be performed. In documented cases where archival material is not available, if agreed between the Investigator and Sponsor, the subject may have a fresh biopsy performed to serve as archival tissue (Section 7.1).

8.10.1.2. Fresh Biopsy Collection

As described above, multiple markers will be reviewed in fresh tissue. All subjects enrolled to Parts C, D, F, G, and H will require a pre-treatment fresh biopsy. Subjects enrolled to Parts C and F will also require a fresh biopsy post-treatment with JTX-2011. If, in the opinion of the investigator, a subject does not have a tumor lesion that can be biopsied at acceptable risk, exceptions may be made by obtaining approval from the Sponsor and Medical Monitor.

Upon confirmed progression, an optional fresh biopsy may be collected at the discretion of the investigator for further analysis.

8.10.2. Retention of Samples

If allowable by local guidelines and/or policies, all blood, PBMCs, and tumor tissue samples will be retained for potential additional testing at a later date or to enable development of a companion diagnostic that would help to identify subjects most likely to benefit from JTX-2011 in the future.

Samples will be retained at a secure storage facility (to be selected, qualified, and contracted by Jounce Therapeutics) in case there is need for retesting. At the end of ten (10) years (or some other period based on local guidelines and/or policies), or if Jounce no longer requires the samples, they will be destroyed. Analyses may be conducted by Jounce Therapeutics, Inc. or by a designated lab at their discretion.

Biospecimens will not be labeled with any personal identifiers (e.g., date of birth, initials). They will be labeled with the subject's study number to allow for future exploratory research analyses to be correlated to the study data and treatment/dose assignments.

8.11. 12-Lead ECG

ECGs will be analyzed locally and data must be reported in the eCRF.

8.12. Urinalysis

A dipstick urinalysis will be performed at Screening, Cycle 1 Day 1, and Day 1 of each additional cycle. Urinalysis testing to include: glucose, blood, protein, bilirubin, ketones, leukocytes and pH. If the dipstick is abnormal a microscopic evaluation will be performed.

8.13. Pregnancy Test

A serum pregnancy test must be performed on all women of child-bearing potential (WOCBP) during the Screening Period and prior to every dose of study drug.

8.14. Adverse Events and Serious Adverse Events

The investigator is responsible for the detection and documentation of events meeting the criteria and definition of an adverse event (AE) or serious adverse event (SAE) as provided in this protocol.

8.14.1. Definition of an Adverse Event (AE)

An AE is any untoward medical occurrence in a clinical investigation subject administered a pharmaceutical product and which does not necessarily have to have a causal relationship with this treatment.

An AE can therefore be any unfavorable and unintended sign (including clinically significant abnormal laboratory finding), symptom, disease, or exacerbation of a pre-existing condition temporally associated with the use of study drug, whether or not related to the study drug.

Disease progression should not be recorded as an AE/SAE. New or increasing symptoms related to disease progression should be reported as an AE or AEs. When possible, the primary diagnosis of the event meeting SAE criteria should be recorded as the AE/SAE term. (For instance, if a patient is hospitalized for shortness of breath and it is confirmed that this is a symptom of a malignant pleural effusion, then malignant pleural effusion should be reported as the event term, rather than disease progression).

8.14.2. Observation and Recording of AEs

The subject will be required to report any AE that occurs after the main informed consent is signed. SAEs will be reported as outlined in Section 8.16 and recorded in the AE CRF. AEs or SAEs occurring after a subject signs the pre-screening ICF will not be collected.

Study personnel will assess AEs at every visit. The date of onset and resolution (if applicable) of the AE will be documented in the source documents and on the appropriate CRF page. The Investigator will monitor all AEs to the final visit or to a satisfactory resolution if the AE is ongoing.

All AEs will be recorded from the time of signed informed consent until the End of Treatment visit (28 days \pm 7 days after the last dose of JTX-2011, nivolumab, ipilimumab, or pembrolizumab, whichever occurred last), and are to be recorded on the appropriate AE pages in the eCRF and in source documents. AEs for the End of Treatment visit may be collected by a telephone contact if the patient is not able to attend an on-site End of Treatment visit. Where possible, a diagnosis rather than a list of symptoms should be recorded. If a diagnosis has not been made then each symptom should be listed individually.

All study drug related AEs/serious adverse events (SAEs) (see Section 8.16 for definition) will be followed to resolution (the subject's health has returned to his/her baseline status or all variables have returned to normal), or until new therapy initiated. Where appropriate, medical tests and examinations will be performed to document resolution of the event(s).

SAE Reporting Contact Information

Tel: [REDACTED]

Fax: [REDACTED]

Email: [REDACTED]

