5.6. Part D (JTX-2011 in Combination with Nivolumab Combination Phase 2)

Part D will include approximately 15 subjects in each of 6 dose expansion cohorts (90 total subjects) in the indications listed below of JTX-2011 in combination with nivolumab at a JTX-2011 dose of 0.3 mg/kg:

q3w JTX-2011 + q3w nivolumab

- D01: HNSCC that has progressed on or after a prior PD-1 inhibitor
- D02: NSCLC that has progressed on or after a prior PD-1 inhibitor
- D03: TNBC
- D04: Melanoma that has progressed on or after a prior PD-1 inhibitor (*closed to enrollment*)
- D05: Gastric cancer or gastroesophageal junction adenocarcinoma
- D06: MSI-H or dMMR endometrial cancer (*closed to enrollment*)

The JTX-2011 dose in Part D is 0.3 mg/kg. Subjects in Part D expansion cohorts D01, D02, D03, D04, and D05 will be stratified based on ICOS expression by IHC in archival tumor, with ICOS levels confirmed on a fresh pre-treatment biopsy. At least 10 subjects with high (2+ to 3+) ICOS expression will be enrolled in each 15-subject cohort to explore potential correlation between pre-treatment ICOS expression and efficacy. More subjects may be enrolled to ensure a minimum 10 subjects with high ICOS expression. Additional potential predictive biomarkers will also be evaluated.

Fresh pre-treatment biopsies will be examined retrospectively to assess correlation of potential predictive biomarkers with efficacy.

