6.9. Pre-Screening for ICOS Expression

Subjects who have archival biopsy samples available for submission to the central lab for measurement of ICOS expression may provide informed consent for submission of archival samples for evaluation prior to undergoing the informed consent process and screening for full study participation. A separate abbreviated Informed Consent Form will be provided to sites to utilize for this purpose upon approval by their governing IRB. In situations where a subject's archival samples are completely exhausted, subjects may elect to have a biopsy performed per institutional guidelines to serve as an archival sample. Results from ICOS testing of archival tissue performed prior to the 28-day screening window will not need to be repeated.

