8.16.4. Observation and Recording of SAEs

All SAEs must be reported to Novella within 24 hours of first awareness of the event.

Additional follow-up information, if required, or available, should be recorded on a follow-up SAE Report Form and faxed to Novella Drug Safety within one business day of discovery by site.

All SAEs, whether related or unrelated to study drug, will be recorded from the time of signed informed consent until resolution or new therapy initiated or for 28 days post final dose if no new therapy is initiated. Any SAEs considered to have at least a possible relationship to the study drug and discovered by the Investigator at any time period after the subject's study treatment has ended should be reported according to the timeframe described above.

Study drug-related SAEs will be followed until resolution, stabilization or subject receives new therapy.

At a minimum, the site number, Investigator's name, subject number, event name, the date of onset, a short description of the event and the Investigator's preliminary assessment of causality must be provided at the time of the initial SAE report.

The onset date of the SAE is defined as the onset date of signs and symptoms or a change in baseline when the SAE met seriousness criteria.

The resolution date of the SAE is defined as the date in which the criteria of seriousness is no longer applicable (e.g., discharge from hospitalization).

All SAEs that are ongoing events at the time of death should be considered not resolved at time of death.

The Investigator is encouraged to discuss with the Medical Monitor any SAEs for which the issue of reportability is unclear or in question.

The Investigator must review, sign, and date the SAE Report Form to confirm the accuracy of the information recorded on the SAE Report Form along with the corresponding source documentation.

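### Serious complications of a substitute biopsy taken during ICOS pre-screening, before main consent, fall outside the sponsor's SAE collection

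*Protocol*

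**What the plan says.** Protocol 6.9 sets up ICOS pre-screening under a separate, shortened consent form. Its purpose is "submission to the central lab for measurement of ICOS expression", and it takes place "prior to undergoing the informed consent process and screening for full study participation". If the archival material is used up, "subjects may elect to have a biopsy performed per institutional guidelines to serve as an archival sample".

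Protocol 8.14.2 fixes when event reporting begins: "The subject will be required to report any AE that occurs after the main informed consent is signed". For the period before that it says: "AEs or SAEs occurring after a subject signs the pre-screening ICF will not be collected".

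Protocol 8.16.4, the SAE section, says: "All SAEs, whether related or unrelated to study drug, will be recorded from the time of signed informed consent". It does not say which of the two consents is meant.

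Protocol 8.10.1.1 describes a similar replacement biopsy when archival material is unavailable. There it needs agreement between investigator and sponsor, and the text refers to Section 7.1, the main screening visit.

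**The concern.** Not collecting events is sensible when pre-screening means shipping a stored tissue block, because nothing is done to the person. It fits less well when the same section permits a new invasive procedure to supply the sample. The protocol itself treats biopsy as carrying risk. Parts C, F, G and H allow the biopsy requirement to be waived where the health risk would be unreasonable, and 8.10.1.2 allows exceptions where no lesion can be biopsied at acceptable risk.

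What is at stake is subject protection and the record of procedural safety. Someone who has a serious complication may not go on to sign the main consent. The loss could therefore fall on the people with the worst outcomes, although the documents give no data on this.

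**Working it through.** No arithmetic applies, so the check is whether any provision brings such an event back into the sponsor's data.

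1. **Can a biopsy precede main consent?** Yes under 6.9. The biopsy sentence sits inside the pre-screening section, and that step comes before the full consent process.
2. **How long can the interval be?** No upper limit is given. 6.9 adds: "Results from ICOS testing of archival tissue performed prior to the 28-day screening window will not need to be repeated". Testing can therefore come earlier than the 28-day screening period.
3. **Does 8.14.2 make an exception?** No. SAEs are named in the exclusion, and procedure-related events are not carved out.
4. **Does 8.16.4 restore collection?** Not clearly. Its starting point is a signed consent that it does not identify, while 8.14.2 deals with the pre-screening form by name. The more specific sentence would normally govern.
5. **Does 8.10.1.1 restore it?** Only for a biopsy done by that route. Section 7.1 lists signing the consent form as its first item, so a biopsy done there falls within collection. The 6.9 route carries no such reference and asks for no sponsor agreement. Whether a similar complication is recorded depends on which section the site followed.
6. **Does the SAP restore it?** No. SAP 3.2.1 takes safety data from enrolment to 28 days after the last dose.
7. **Does it reach the SMC?** No route is given. The data that the SMC reviews under Protocol 6.1 are study safety data, and 8.14.2 keeps this event out of them.
8. **Does it reach an IRB?** Possibly. Protocol 8.17 asks the investigator to report significant risks to subjects, and site SAEs according to site guidelines. Protocol 11.1 asks that the IRB be kept informed of serious and significant AEs. Neither is limited to events after main consent.

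The gap therefore runs from the pre-screening consent to the main consent, and it also covers people who never sign the main consent.

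**Who is exposed.** The route matters most where the archival result drives enrolment. In Part D, cohorts D01 to D05 "will be stratified based on ICOS expression by IHC in archival tumor", and D04 is closed. Cohort C07 counts archival scores towards completing enrolment (Protocol 5.5), although SAP Section 4 describes Part C as C01 to C05. Pre-screening is not required in Parts C, F and H. Parts A and B have completed enrolment, and SAP Section 4 records that Parts F and H never opened. The share of people with exhausted tissue, the number who chose a biopsy and the complication rate are not given, so no event count can be derived.

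**The case against.** The strongest case on the other side has four parts.

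- **No trial result changes.** The safety set is treated subjects, relatedness is judged against study drug, and only treatment-emergent events are summarised. An event before dosing would not inform a dose decision. This stands in full: the point concerns subject protection and procedural safety, not the analysis.
- **The biopsy is elective and follows institutional practice.** This limits how often it occurs. It does not make the procedure independent of the trial, since 6.9 offers it so that a sample can be supplied.
- **The text does not say which consent covers the biopsy itself.** A reader might infer that it is done under the abbreviated form. 6.9 describes that form as covering submission of archival samples and is silent on consent for the procedure. The form is not among the documents reviewed, so what it says about biopsy risk or injury reporting is unknown. The point does not need that inference, because 8.14.2 turns on when the event occurs.
- **8.10.1.1 already places the replacement biopsy at main screening.** This is partly right, and it shows that the two sections disagree. It does not close the gap while 6.9 still permits the earlier route.

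**Conclusion.** The gap is real and narrow. Under 6.9 and 8.14.2 read together, a serious complication of a substitute biopsy that occurs before main consent, or in a person who does not enrol, is outside the sponsor's SAE collection and the SMC's view. This results from a stated rule, not from missing detail.

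The conclusion rests on two readings: that the 6.9 biopsy takes place during pre-screening, as its position in the protocol implies, and that the specific exclusion in 8.14.2 prevails over the general wording of 8.16.4. The size is unknown and probably small.

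Three stronger readings are tempting, and the documents do not support them:

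- A reader might infer that events in pre-screened people are lost for good. Events with onset after main consent are collected under 8.14.2, even though the exclusion sentence states no end point.
- A reader might infer that the biopsy serves the ICOS test alone. That is the purpose stated in 6.9, but archival tissue is also assessed for PD-L1 and, if there is enough, for other markers (Protocol 8.10 and 8.10.1.1).
- A reader might infer that IRBs are blind to such harm, or put a figure on the missed SAEs. The local IRB route stays open, and no figure in the documents supports a count.

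**What to change.** - **8.14.2:** keep the exemption for submission of existing tissue. Add that when a substitute biopsy is performed under 6.9, SAEs considered related to it are collected from the procedure until main consent or the end of a stated short follow-up, using the existing SAE form.
- **8.16.4:** add the matching line, and name the consent that starts SAE recording in general.
- **Identifier:** give pre-screened subjects one. The initial SAE report requires a subject number, and the documents do not say that these people receive one.
- **6.9 and 8.10.1.1:** reconcile them on whether the biopsy may precede main consent and whether sponsor agreement is needed. Requiring main consent before any substitute biopsy would be another way to close the gap.
- **Clinical study report:** list any such events separately from the treatment-emergent tables.

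The cost is a protocol amendment with IRB approval (Protocol 11.5), a possible revision of the abbreviated consent form, which also needs IRB approval (11.1), and a little extra reporting. No procedure is added for subjects.
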